Human Subjects Protocol

Ann Arbor VA Healthcare System IRB

COVID-19 Observational Research Collaboratory

Funding Agency: VA HSR&D

Principal Investigator: [name], PhD, MHS

Version 7, December 16, 2024

Abstract

Background: Early evidence suggests that the frequency and type of long-term complications stemming from SARS-CoV-2 infection may depend on the severity of initial presentation. However, additional unidentified factors may also play a role including those related to the individual, the environment and/or the specific strain of the virus. The long-term health impacts of SARS-CoV-2 will have major implications for health care utilization, care processes and quality and costs of care for Veterans, both within the VA and in the community. Over 200,000 Veterans have had COVID-19. Although the long-term consequences of this novel illness are unknown, it is clear they will often be significant. Our overarching goal in the Long-Term Outcome Study (LTO) is to advance VA HSR&D research into the consequences and care of COVID-19 infection by developing and releasing integrated multi-modal data and results on long-term outcomes of COVID for use by VA clinical, research and operations communities. We will do so via a coordinated program of data production and analysis using the VA electronic health record (EHR) and other administrative sources (e.g., Medicare), de novo longitudinal survey, and qualitative inquiry. This work will be closely coordinated with the COVID-19 Observational Research Collaboratory (CORC) Coordinating Center (CCC) and the burgeoning community of HSR&D-funded COVID researchers.

This study aims to examine the long-term outcomes in Veterans infected and uninfected with SARS-CoV-2.

Aim 1: Using VINCI-CDW data, patients will be identified who had a SARS-CoV-2 test since February 2020. We will use a combination of traditional epidemiologic studies, and machine learning algorithms to determine the long-term, multi-systemic and functional adverse outcomes and/or syndromes related to SARS-CoV-2. Members of the research team are currently developing methods to identify new onset and exacerbations in comorbidities following SARS-CoV-2 illness in Veterans.

Aim 2: Determine Veteran-Reported Outcome Effects Using Structured Survey on domains such as self-reported symptoms, disability, and financial impacts, measured repeatedly over 36 months.

List of Abbreviations

ACEI angiotensin-converting enzyme inhibitors

9.	Information Security and Data Storage/Movement	202
10.	. References	235

Protocol Title: COVID-19 Observational Research Collaboratory

1. Introduction

The majority of patients infected with SARS-CoV-2 develop relatively mild, self-limiting, flu-like symptoms that do not require hospitalization. However, a small proportion develop severe viral pneumonia and hypoxemia, which may progress to respiratory failure, ARDS, cytokine release syndrome, multiorgan failure and death. These patients need hospitalization, frequently require admission to the intensive care unit, often need mechanical ventilation, and have a high mortality.

The COVID-19 pandemic has evolved so quickly that it is still unclear what proportion of infected patients experience adverse outcomes such as hospitalization, ICU admission, mechanical ventilation and death. It is also unclear why a small minority develop severe, life-threatening COVID-19 while the majority have mild or even asymptomatic presentation.

Furthermore, it is becoming apparent that many patients continue to experience symptoms and adverse effects from COVID-19 infection for a long period of time after the acute symptoms subside, a condition known as long COVID. A particular interest of this project is to evaluate the long-term manifestations and outcomes of SARS-CoV-2.¹⁻⁹ The literature so far suggests the following:

- Long-term adverse outcomes may occur not only among survivors of severe acute COVID-19 illness, but among the much larger group who were asymptomatic or minimally symptomatic at presentation.
- A variety of multi-systemic long-term complications are being described related to direct tissue invasion via ACE2 receptors (e.g. lungs, heart, kidneys, CNS), immunologic activation and/or hypercoagulability.
- Early evidence suggests that the frequency and type of long-term complications may depend on the severity of initial presentation. However, additional unidentified factors may also play a role including those related to the individual, the environment and/or the specific strain of the virus.
- Some individuals appear to have persistent symptoms (e.g., fatigue, joint pain and cognitive dysfunction) after clearing the virus ("COVID long haulers"). 10,111 It is not known how prevalent this potential new syndrome might be, the timeline, extent and reversibility of clinical manifestations.
- A "post-ICU" syndrome has been described among survivors of sepsis, respiratory failure, and SARS-CoV and MERS-CoV including decrements in cognitive and physical function, psychological health, quality of life and loss of independence^{12,13} but has not been well characterized in SARS-CoV-2.
- The long-term health impacts of SARS-CoV-2 will have major implications for health care utilization, care processes and quality and costs of care for Veterans, both within the VA and in the community.

For Aim 1, We propose to use national VA electronic data derived from the Corporate Data Warehouse to extract the electronic health records of all VA patients who tested positive for SARS-CoV-2 as well as appropriate control VA enrollees who were in care at the same time but did not test positive for SARS-CoV-2, to determine the rate of adverse outcomes, identify independent predictors and develop innovative, state-of-the-art prediction models of adverse outcomes, evaluate the effectiveness of pharmacotherapies on adverse outcomes and evaluate the impact of SARS-CoV-2 on healthcare utilization.

Aim 2 is a prospective survey of Veterans that has been funded by national HSR&D as a part of the COVID-19 Observational Research Collaboratory (CORC). The CORC is an integrated suite of activities includes secondary analyses of data, the development of this survey (submitted for review here), and other activities not yet progressed to the level of human subjects research and/or being led at other centers. Because the needs of Veterans continue to evolve across the epidemic, all CORC research could not be pre-planned—instead, the project had to be divided

into multiple phases. The CORC team, all the way up to HSR&D Director [name], recognize that this places additional burdens on review process, and are grateful for your flexibility.

The primary scientific question of Aim 2 is "what are the effects of having gotten COVID-19 among Veteran survivors?" In this specific proposal, this question will be answered by comparing a random sample of Veteran survivors of COVID-19 to carefully matched non-COVID Veterans who had the same risk of acquiring COVID, but did not. Our primary outcomes are disability, health-related quality of life, mobility, caregiving receipt, financial hardship, and non-VA healthcare use.

The human subjects research aspects of this work will be conducted exclusively at VA Ann Arbor by approved study team members.

We wish to emphasize that while the application of these techniques to the specific population of Veterans with COVID is highly novel, the techniques themselves are not. They have been developed over the last 10 years at VA Ann Arbor in the study of patients who survived in-hospital cardiac arrest, where they have been highly informative. These techniques for identifying relevant Veterans, contacting them, seeking verbal informed consent, using a brief survey instrument, and following them up over time have all been previously reviewed in detail by AAVA's RDC and IRB as part of IIRs: 1) ResCU I [IIR 13-079] and ResCU II [IIR 17-045], and approved and re-approved as part of continuing review.

[figure not shown]
Aim 2 will utilize the VA Corporate Data Warehouse (CDW) secondary data analysis from Aim 1 to identify all Veterans to be surveyed. These data will come from the CDW and is secured under a HIPAA waiver.

Scientific Background

Scientifically, it has become increasingly clear that patients who survive the illness caused by SARS-CoV-2—that is, COVID-19—have a wide range of ongoing concerns. Whereas once some assumed the COVID-19 would be rapid but self-limited illness (ending in either mortality or recovery), it is instead clear that something is still going on with these patients. Lay press reports have termed this "Long COVID" or "Long-Haulers", and have framed it as consistent with other post-illness syndromes or as something entirely new and different. A robust online community has evolved (e.g. https:// www . survivorcorps . com) and the CDC has begun doing education about its existence (https:// www .cdc.gov /coronavirus/2019-ncov/long-term-effects.html). The NIH has announced a major call for research into Post Acute Sequelae of COVID. By October 2020, del Rio, Collins, and Malani reviewed potential long-term consequences in JAMA and noted potential sequelae in nearly every organ. The United Kingdom's National Institute for Health and Care Excellence, the Scottish Intercollegiate Guidelines Network, and the Royal College of General Practitioners have already endeavored to release guidelines for Long-COVID, and these have been critiqued seems to omit any awareness of non-immunologically mediated consequences of illness. No generally accepted case definition or consensus theory of "long-term outcomes" exists yet.

This may be, in part, because population-based surveillance has been woefully rare to this point, and what is out there has recreated nearly every form of bias in measurement described in any epidemiologic text—particularly highly selected samples with substantial non-random missingness in outcome

Figure 1. Readmission or death after COVID-19 in VA, Spring 2020

ascertainment. Within these selected samples, there is often a very substantial focus on specific symptoms. 6-month follow-up from Spring 2020 survivors in Wuhan emphasized fatigue, weakness, and depression, albeit in follow-up limited to among those without readmission to the hospital or any mobility impairment. A January 2021 report from Northern Italy noted frequent substantial impairments in respiratory function and mental health

among survivors of COVID, yet also a 65% refusal-to-participate rate.¹⁴ Frequent worsening of mental health and limited access to care were noted among respondents to an online convenience sample of Canadians.¹⁵

What U.S.-based population-based data are available raise troubling signals. A multi-state follow-up of patients with a positive COVID test from spring 2020 found that a third had not returned to work 2-3 weeks later. ¹⁶ Similar rates are being seen in a new national cohort study funded by NHLBI. (unpublished data) While a report from a single home health company in New York City suggested dramatic early improvements ¹⁷, patients hospitalized at 38 hospitals in Michigan from the spring 2020 wave were followed for 60-days and found 38% were still unable to return to their normal activity, 49% reported mental health effects of their illness, 23% had lost a job because of their illness and its sequelae, and 37% reported negative financial impacts of their illness; yet this study was only able to follow-up 42% of those alive and whom it attempted to contact. ¹⁸ We recently have shown in a JAMA article ¹⁹ that Veterans with COVID-19 (n=2,179) have an increased risk of readmission or death in the 10-days but not 60-days after discharge compared to matched patients with pneumonia or heart failure. (Figure 1) Of those readmitted, the most common readmission diagnoses were COVID-19 (30.2%), sepsis (8.5%), pneumonia (3.1%), and heart failure (3.1%). During readmission, 22.6% were treated in ICU, 7.1% were mechanically ventilated, and 7.9% received vasopressors. Readmission problems after COVID were of the same order of magnitude as readmission problems after pneumonia or heart failure—well-established problems of impact.

The exponential growth of the COVID-19 literature makes a more comprehensive overview both impossible and outdated by the time it is finished. Interpreting the above key findings in the COVID-19 literature in light of existing literature on long-term outcomes of other acute infectious diseases^{1,2,12,20} identifies gaps in the literature not likely to be filled by other groups, emphasizing VA HSR&D's comparative advantages.

First of all, it makes it clear that measuring the long-term outcomes of COVID-19 among Veterans is not a trivial task. Depending on the purpose, that question must be operationalized in different ways.

- For a clinician running a post-COVID clinic, the central issue is: what are the range and expected frequencies of health problems that a Veteran coming to the clinic may have?
- For those seeking to understand the natural history of COVID-19, the central issue is: what would the patient's life have been like if they had not been infected with SARS-CoV-2?
- For those studying recovery from acute illness, the central issue is: what is distinctive about COVID-19 recovery relative to other recoveries from equally severe acute illnesses?
- For those charged with planning for health systems, the central issues may be: what can be done to prevent future harm, improve the recovery of those who have already recovered from COVID-19, and plan for the ongoing healthcare needs of those still in recovery?
- For Veterans recovering from COVID-19, their families and those who care for them: what are they to expect in the future and what is the experience of having long-term complications of COVID-19 like?

The problems that patients with COVID-19 face represent the culmination of multiple different factors and dynamic processes:

- SARS-CoV-2-specific damage and recovery
- Treatments for COVID-19 and associated complications
- 2020/2021 surge-related changes in access to and quality of care
- 2020/2021 economic and social disruptions
- Their pre-existing health, access to care, and social supports and environment

Because COVID-19's distribution is non-random among Veterans—and the fundamental implications of this observation²¹⁻²³ is easy to overlook—identifying the "outcomes" of COVID-19 is not a trivial task. We propose approaches to disentangle these factors in ways relevant to the key users above. We also propose that the past literature has largely missed a focus on the distinctive issues of health services research. Past work has focused on specific symptoms and organ dysfunction, rather than taking a patient-centered approach that puts overall health needs and ability to participate in work and life at the center of the exploration. Such organ-specific science is incredibly important, but also risks missing the issues that are driving central decrements of quality of life; moreover, other groups outside of HSR&D are extensively investing in it. In many cases, not enough time has elapsed yet to understand the outcomes of COVID-19. Furthermore, past work on "big picture" recovery has overwhelmingly not had an explicit comparison group, or a comparison group matched in a relatively non-specific way. Given the non-randomness of COVID infection²¹, including its fundamental racial, ethnic²⁴, geographic, and temporal variation²⁵, this means that often past work is unable to disentangle what is caused by COVID and what is caused by the other co-incident factors outlined above. We propose to correct some of these deficits.

2. Objectives

Aim 1

- 1. Determine the long-term multi-systemic and functional adverse outcomes of SARS-CoV-2 infection in the Veteran population
- 2. Determine risk factors and develop prediction models for the development of long-term adverse outcomes of SARS-CoV-2 to support risk stratification, mitigation, targeted outreach, preventive measures and treatment.
- 3. Evaluate the effectiveness of pharmacotherapies on the development of short- and long-term adverse outcomes of SARS-CoV-2 infection.
- 4. Evaluate the impact of SARS-CoV-2 on healthcare utilization, care processes and costs to estimate current and future health system needs related to COVID-19.

Aim 2

The challenge of COVID-19 is unequaled in magnitude; it is not, however, without precedent. VA clinicians have saved—and continue to save—thousands of lives by grounding their care in decades of research on viral pneumonia, sepsis, acute respiratory distress syndrome (ARDS), and infection control. While much is unknown, this proposal is informed by decades of rigorous research on the long-term consequences of acute infection,¹⁻⁵ while identifying distinctive features of COVID-19. Around Thanksgiving 2020, when we began preparing this proposal, the VA estimated approximately 100,000 Veterans had been stricken by COVID-19; that estimate as of President's Day 2021 is now over 220,000. These Veterans deserve research that is rigorous, reproducible, and relevant to inform efforts to enhance their long-term recovery. Lessons learned in the VA will benefit the wider nation. We have structured our proposal to be able to serve the Veterans already struck with COVID-19 while able to adapt to changing scientific priorities as the pandemic continues.

Our overarching goal in the Long-Term Outcome Study (LTO) is to advance VA HSR&D research into the consequences and care of COVID-19 infection by developing and releasing integrated multi-modal data and results on long-term outcomes of COVID for use by VA clinical, research and operations communities. We will do so via a coordinated program of data production and analysis using the VA electronic health record (EHR) and other administrative sources (e.g., Medicare), de novo longitudinal survey (this study), and qualitative inquiry. This work will be closely coordinated with the COVID-19 Observational Research Collaboratory (CORC) Coordinating Center (CCC) and the burgeoning community of HSR&D-funded COVID researchers. Philosophically, we believe in four co-equal metrics of success: (1) novel discoveries published in the scientific literature; (2) usefulness of our work to VA operational partners; (3) use of our work as foundation and support for other VA investigators in their own work; and (4) giving voice to Veterans experiences and challenges in recovery from COVID-19.

In this proposal, our driving scientific question throughout is: "What is the effect on Veterans of a COVID-19 infection compared to not having gotten COVID-19 at that time?" We focus on the first 36 months after COVID-19.

Aim 2, Determine Veteran-Reported Outcome Effects Using Structured Survey. Examine and compare a population of Veterans recovering from COVID illness with a population with no positive COVID test or treatment in the VA regarding self-reported symptoms, disability, informal caregiving receipt, and financial impacts, using a structured survey approach and linked with routinely collected administrative and clinical data. We will describe effects, moderators, and causal effects via repeated surveys.

5. Study Procedures

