patient's first positive test. We will conduct stratified random sampling with differential survey weights so that cases are equally divided based on maximal severity of their acute COVID course in VA to include members of the following mutually exclusive groups based on patterns of health care utilization within the first 30 days after initial infection with SARS-CoV-2: not hospitalized in VA; hospitalized in VA but not mechanically ventilated; mechanically ventilated. Stratified random sampling with variable sampling weights offers two advantages: (1) sampling weights assure that the aggregated population results are still representative of the study population as a whole; while (2) ensuring adequate representation to support comparisons across these subgroups of interest. Stratum- and wave-specific sampling fractions will be chosen based on data on survival to the relevant time-point in.

In general, we will organize the sampling of cases (and later of comparators) around the waves of the epidemic, as defined by their nadirs between national death rates—each approximately 3-4 months long, as shown in Figure 2 generated based on data from the COVID tracking project. As shown in Table 3, we will initiate surveys of Veterans who have survived their initial SARS-CoV-2 infection. The viral infection "index date" will be defined as date of each patient's first positive test. This will be a longitudinal survey such that once we start surveying a Veteran, that same Veteran will be surveyed in later waves as well—we will not "resample" between, for example, the 12- and 24-month surveys.

Comparators: To support causal inference, we will also sample Veterans without COVID who are matched to participants with COVID-19. In general, cases will be compared to comparators matched on risk of developing COVID infection during a given wave, incorporating geography at the VAMC and VISN level to take into account spatiotemporal heterogeneity and small area variations. There are certain nuanced issues around precise definitions of pseudo-index dates for comparators, and particularly avoiding immortal time bias, to which we will closely attend during implementation with the input of the Methods Core. In general, we will use coarsened exact matching or propensity scores to ensure balance on key measurable covariates, both of which our group has substantial experience with.

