Analytic Methods: Descriptive: We will summarize each of the outcomes listed in Table 2 for the patient cohort at each 6-month after the index illness. Summary statistics (mean, median, mode, range; frequency; missing data) will be reported in tabular and graphical format. Survey weights will be incorporated throughout to allow generalizability of estimates to the source Veteran population receiving VA primary care.

Analytic Methods: Variation in Survey Outcomes: A similar approach as in Aim 1 will be used for defining variation in key survey-reported outcomes, albeit with greater constraints on the number of covariates that can be included due to the more limited size of the survey sample. Multi-level models will be estimated after controlling for patient-level factors such as age, race, and summary Elixhauser comorbidity score⁴⁸, and nested within hospitals. Longitudinal growth curve models within respondents over time will be used, as we have before, to examine evolution of outcomes over time.

In general, we expect quite little missing data due to our prior experience with very high item-level completion in administering these specific instruments to Veterans after hospitalization. However, should this be a concern, we will use case-wise deletion or multiple imputation, depending on the frequency of missingness.

Analytic Methods: Causal Effects of COVID on Clinical Outcomes: Our primary causal scientific question is: "What is the effect of a COVID-19 infection compared to not having gotten a COVID-19 infection at that time on patient-reported financial and mental health functioning?"

Patients who experienced (and survived) COVID-19 will be matched to a comparator patient cohort. Causal inference is strengthened by the following strategies: (a) matching patients with and without COVID-19 on key patient characteristics, and ensuring that both groups had equal ability to be selected into the study (e.g., due to survival), (b) administering surveys on the same timeframe between COVID-19 patients and comparators, relative to a selected index date/time zero, (c) collecting sufficient data on key covariates that are unmeasured in the EHR and guided by directed acyclic graphs (DAGs) and other causal graphs generated in collaboration with the CORC's Methods Core, (d) accounting for those covariates through inverse probability of treatment weights or similar approaches.

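### Aim 2 asks for the effect of infection without a survival condition in two places, but the survey contrast covers only Veterans alive at the survey, and no handling of death is defined

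*Protocol*

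**What the plan says.** The Aim 2 question appears in two forms.

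- **Conditional on survival.** The protocol Introduction gives the primary question as "what are the effects of having gotten COVID-19 among Veteran survivors" and plans to answer it by "comparing a random sample of Veteran survivors of COVID-19 to carefully matched non-COVID Veterans".
- **Not conditional.** Section 2, Objectives (Aim 2) asks "What is the effect on Veterans of a COVID-19 infection compared to not having gotten COVID-19 at that time" and calls this the driving question throughout. Section 5.1, under the causal effects methods, opens its primary causal question with "What is the effect of a COVID-19 infection compared to not having gotten a COVID-19 infection at that time". The Scientific Background also lists, for natural history, "what would the patient's life have been like if they had not been infected with SARS-CoV-2".

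On survival and selection, the protocol says the following.

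- Section 5.1 restricts the surveys to cases who survived the initial infection. Section 5.2 has vital status checked in CDW before every contact, for cases and comparators alike.
- Section 5.1 lists four strategies said to strengthen causal inference. The first includes "ensuring that both groups had equal ability to be selected into the study (e.g., due to survival".
- Cases are to be split equally into not hospitalized, hospitalized and ventilated. "Stratum- and wave-specific sampling fractions will be chosen based on data on survival to the relevant time-point" (the sentence breaks off there).
- The Introduction says that patients with severe illness "often need mechanical ventilation, and have a high mortality". It gives no rate.
- Section 5.8 names mortality as an Aim 1 outcome.

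In the SAP, the first IADL survey is at 18 months. The Analysis section specifies a linear mixed model with a COVID-by-time interaction, adjusted for age, sex and CAN score. The SAP does not mention death or survey weights.

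**The concern.** Survival to the first survey is decided after infection and can be changed by it. Suppose cases and comparators are equally frail at the index date on everything that was not measured. If infection then kills some of the frailer cases, the cases still alive at 12 or 18 months are on average less frail than the surviving comparators. Applying the same survival rule to both groups does not undo this, because the rule removes different people from each.

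Two things are at stake. First, a difference between survivors would be reported as the answer to a question about infection as such. Second, the distortion would tend to make cases look better than they should, so a finding of no excess limitation could be read as no long-term effect when fewer infected Veterans are alive and independent. The SAP Background already reports no excess limitation at 18 months, and without deaths by group a reader cannot judge how far selection contributed.

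Even the narrower question in the Introduction needs a definition. A plain survivor-against-survivor difference is not automatically the effect in people who would have survived either way.

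**Working it through.** **The plan's own figures.** Six months x 100 = 600 cases sampled, and 235/600 = 39.2%, as the SAP states. The 365 sampled cases who did not complete (60.8%) are not divided into deaths and other reasons. Neither document gives a death rate for Aim 2, so everything below is illustrative.

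**Assumptions.**

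- Deaths by 18 months: 5% in comparators, 5-6% in non-hospitalized, 20-25% in hospitalized and 40-55% in ventilated cases.
- Frailty left after matching is N(0,1) in every group at index. One SD multiplies the odds of death by 1.5 to 3 and adds 1.2 limitations.
- Infection has no true effect on limitations, and the SD of the count is 3.

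**Bias among survivors.** For each group the intercept *a* of logit P(death | u) = a + ln(OR) x u is set to give the assumed death rate. The mean of u among the living is then computed by numerical integration. Bias = 1.2 x (mean in surviving cases - mean in surviving comparators).

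| Group | Frailty difference (SD) | Bias (limitations) |
|---|---|---|
| Hospitalized | -0.06 to -0.18 | -0.07 to -0.21 |
| Ventilated | -0.14 to -0.43 | -0.16 to -0.52 |
| Equal thirds, unweighted | -0.07 to -0.21 | -0.08 to -0.25 |
| Assumed 83/15/2% severity mix | -0.01 to -0.04 | -0.01 to -0.05 |

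In the last row, the far end is -0.04 if the mix describes the living and -0.05 if it describes cases at index.

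**Against sampling error.**

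- SAP sample: 3 x sqrt(1/235 + 1/244) = 0.27. The severity-weighted bias is about 4% to 19% of that.
- Protocol Table 3: 3 x 400 = 1,200 cases and 3 x 200 = 600 comparators, so 400 cases per severity third. SE for one third against all comparators = 3 x sqrt(1/400 + 1/600) = 0.19. The bias is then about 0.4 to 1.1 SE for hospitalized and 0.8 to 2.7 SE for ventilated cases.
- All thirds pooled without weights: SE = 3 x sqrt(1/1200 + 1/600) = 0.15. The bias is about 0.5 to 1.7 SE.

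**What a survivors-only null can hide.** Suppose half of the living in each group have no limitation. The survivors-only difference is 0. The difference in the proportion alive without limitation is 0.5 x (case survival - 0.95):

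- hospitalized: 0.5 x (0.80 - 0.95) = -7.5 points, to 0.5 x (0.75 - 0.95) = -10 points;
- ventilated: 0.5 x (0.60 - 0.95) = -17.5 points, to 0.5 x (0.45 - 0.95) = -25 points;
- 83/15/2% mix: case survival 92.1% to 90.2%, so -1.5 to -2.4 points.

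**Width of survivor bounds.** Assume infection never prevents a death and the outcome is normal. The share trimmed from surviving comparators is q = 1 - (1 - m1)/(1 - m0), where m1 and m0 are the death rates in cases and comparators. The half-width is phi(z_q)/(1 - q) SD. This gives 0.07 SD at 5% v 8% deaths, 0.29 at 5% v 20% and 0.52 at 5% v 35%.

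**Direction.** The negative sign depends on equal residual frailty at index. If hospitalized cases began 0.06 to 0.18 SD frailer, or ventilated cases 0.14 to 0.43 SD frailer, the bias would be cancelled, because those are the survivor differences in the table. Larger starting differences would reverse it.

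**The case against.** Several points on the other side stand.

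- The Introduction already limits the Aim 2 question to survivors, and the causal text in section 5.1 goes on to speak of patients who had and survived COVID-19. Part of the problem is therefore wording that is not carried through.
- Section 5.1 describes comparators matched to participants and to surviving cases. On that description measured frailty is balanced against surviving cases, and mainly unmeasured frailty remains. The planned extra covariates, causal graphs and weighting, and the SAP's adjustment, reduce it further. The SAP does not say whether its monthly matching came before or after survival was known.
- The SAP tests change from 18 to 36 months. Selection before enrolment shifts the 18-month level, and it reaches the slope only if frailty also drives change.
- The SAP sample was stratified by hospitalization, not ventilation, so the largest figures above do not describe it.

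The immortal-time remark in section 5.1 does not answer the point, since it concerns index dates for comparators.

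A reader might also infer more than the documents support:

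- *That depleted cases are set against an almost complete comparator group.* Comparators must also be alive, and neither group's mortality is given.
- *That the study never counts death.* Aim 1 does, and its data can be linked to the survey. What is missing is a tie to the Aim 2 contrast.
- *That sampling fractions are raised for survivors in severe strata.* The text says only that they depend on survival data.
- *That the protocol claims equal eligibility makes the groups comparable.* It says only that this strengthens inference.

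**Conclusion.** The concern holds in a limited form. The survey contrast fits the survivor question in the Introduction but does not identify the unconditional effect asked in the Objectives and in section 5.1. Equal survival eligibility does not close that gap while unmeasured frailty remains and infection affects survival. Neither document defines an estimand under death, a combined outcome or a sensitivity analysis for Aim 2.

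The size is unknown. On the assumed rates the bias is negligible to small in a severity-weighted overall estimate. It could matter in the hospitalized or ventilated strata, or in an unweighted analysis of a severity-enriched sample. It bears mainly on comparisons of level.

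It would go too far to say that survivor selection produced the 18-month null. That result comes from a previous study whose methods are not shown, and the sign of the bias within strata is not established. Non-completion by 365 of 600 cases is a separate selection and may be the larger one.

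**What to change.** 1. In protocol section 2 (Aim 2), the causal text of section 5.1 and the SAP Aim, describe the survey contrast as one *among Veterans alive at the survey*, in line with the Introduction.
2. Report beside it, by survey time and by hospitalization or severity stratum, survival from index date in cases and matched comparators, using CDW vital status.
3. In the same layout, report the proportion alive and without limitation: survival in the parent matched cohort times the survey-weighted proportion without limitation among the living. Show both components.
4. Add a survivor-bounds sensitivity analysis for the hospitalized and ventilated strata, stating the assumption that infection does not prevent deaths.
5. Optionally, add an EQ-5D analysis with death valued at 0.

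The SAP describes its analysis in the past tense, so any additions should be marked as supplementary. The cost is revised wording and a modest amount of analysis. No new data collection is needed, because vital status is already consulted before each contact. The drawback is that a combined outcome mixes death with disability, which is why both components should be shown.
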